15.3.5 Renal irAEs

Grade of Creatinine Increased (NCI-CTCAE v5)	Initial Management	Follow-up Management

Grade 1 Creatinine increased >ULN to 1.5 x ULN
	
Continue avelumab therapy
	
Continue renal function monitoring If worsens: Treat as Grade 2 to 3 or 4.

Grade 2 to 3 Creatinine increased > 1.5 and ≤ 6 x ULN
	
Withhold avelumab therapy Increase frequency of monitoring to every 3 days 1.0 to 2.0 mg/kg/day prednisone or equivalent. Add prophylactic antibiotics for opportunistic infections Consider renal biopsy
	
If returns to Grade ≤1: Taper steroids over at least 1 month, and resume avelumab therapy following steroids taper. If worsens: Treat as Grade 4.

Grade 4 Creatinine increased > 6 x ULN
	
Permanently discontinue avelumab therapy Monitor creatinine daily 1.0 to 2.0 mg/kg/day prednisone or equivalent. Add prophylactic antibiotics for opportunistic infections Consider renal biopsy Nephrology consult
	
If returns to Grade ≤1: Taper steroids over at least 1 month.

15.3.6 Cardiac irAEs

Myocarditis (All grades)	Initial Management	Follow-up Management

New onset of cardiac signs or symptoms and / or new laboratory cardiac biomarker elevations (e.g. troponin, CK-MB, BNP) or cardiac imaging abnormalities suggestive of myocarditis.
	
Withhold avelumab therapy. Hospitalize. In the presence of life threatening cardiac decompensation, consider transfer to a facility experienced in advanced heart failure and arrhythmia management. Cardiology consult to establish etiology and rule-out immune-mediated myocarditis. Guideline based supportive treatment as per cardiology consult.* Consider myocardial biopsy if recommended per cardiology consult.
	
If symptoms improve and immune-mediated etiology is ruled out, re-start avelumab therapy. If symptoms do not improve/worsen, viral myocarditis is excluded, and immune-mediated etiology is suspected or confirmed following cardiology consult, manage as immune-mediated myocarditis.

Immune-mediated myocarditis
	
Permanently discontinue avelumab. Guideline based supportive treatment as appropriate as per cardiology consult.* 1.0 to 2.0 mg/kg/day prednisone or equivalent Add prophylactic antibiotics for opportunistic infections.
	
Once improving, taper steroids over at least 1 month. If no improvement or worsening, consider additional immunosuppressants (e.g. azathioprine, cyclosporine A).

*Local guidelines, or e.g. ESC or AHA guidelines ESC guidelines website: https://www.escardio.org/Guidelines/Clinical-Practice-Guidelines AHA guidelines website: http://professional.heart.org/professional/GuidelinesStatements/searchresults.jsp?q=&y=&t=1001
		

15.3.7 Endocrine irAEs

Endocrine Disorder (NCI-CTCAE v5)	Initial Management	Follow-up Management

Grade 1 or Grade 2 endocrinopathies (hypothyroidism, hyperthyroidism, adrenal insufficiency, type I diabetes mellitus)
	
Continue a velumab therapy
 
Endocrinology consult if needed
 
Start thyroid hormone replacement therapy (for hypothyroidism), anti-thyroid treatment (for hyperthyroidism), corticosteroids (for adrenal insufficiency) or insulin (for Type I diabetes mellitus) as appropriate.
 
Rule-out secondary endocrinopathies (i.e. hypopituitarism / hypophysitis)
	
Continue hormone replacement/suppression and monitoring of endocrine function as appropriate.

Grade 3 or Grade 4 endocrinopathies (hypothyroidism, hyperthyroidism, adrenal insufficiency, type I diabetes mellitus)
	
Withhold a velumab therapy
 
Consider hospitalization
 
Endocrinology consult
 
Start thyroid hormone replacement therapy (for hypothyroidism), anti-thyroid treatment (for hyperthyroidism), corticosteroids (for adrenal insufficiency) or insulin (for type I diabetes mellitus) as appropriate.
 
Rule-out secondary endocrinopathies (i.e. hypopituitarism / hypophysitis)
	
Resume a velumab once symptoms and/or laboratory tests improve to Grade ≤ 1 (with or without hormone replacement/suppression).
 
Continue hormone replacement/suppression and monitoring of endocrine function as appropriate.


Hypopituitarism/Hypophysitis, all grades (secondary endocrinopathies)
	
If secondary thyroid and/or adrenal insufficiency is confirmed (i.e. subnormal serum FT4 with inappropriately low TSH and/or low serum cortisol with inappropriately low ACTH):
 
 • Refer to endocrinologist for dynamic testing as indicated and measurement of other hormones (FSH, LH, GH/IGF-1, PRL, testosterone in men, estrogens in women) • Hormone replacement/suppressive therapy as appropriate • Perform pituitary MRI and visual field examination as indicated 
If hypophysitis confirmed:
 
 • Continue a velumab if mild symptoms with normal MRI. Repeat the MRI in 1 month • Withhold a velumab if moderate, severe or life-threatening symptoms of hypophysitis and/or abnormal MRI. Consider hospitalization. Initiate corticosteroids (1 to 2 mg/kg/day prednisone or equivalent) followed by corticosteroids taper during at least 1 month. • Add prophylactic antibiotics for opportunistic infections. 	
Resume a velumab once symptoms and hormone tests improve to Grade ≤ 1 (with or without hormone replacement).
 
In addition, for hypophysitis with abnormal MRI, resume a velumab only once shrinkage of the pituitary gland on MRI/CT scan is documented.
 
Continue hormone replacement/suppression therapy as appropriate.

15.3.8 Other irAEs

NOTE: This pertains to “other” irAEs (i.e., not described above).

Grade of other irAEs (NCI-CTCAE v5)	Initial Management	Follow-up Management
Grade 2 or Grade 3 clinical signs or symptoms suggestive of a potential irAE	Withhold a velumab therapy pending clinical investigation	If irAE is ruled out, manage as appropriate according to the diagnosis and consider re-starting a velumab therapy If irAE is confirmed, treat as Grade 2 or 3 irAE.
Grade 2 irAE or first occurrence of Grade 3 irAE	Withhold a velumab therapy 1.0 to 2.0 mg/kg/day prednisone or equivalent Add prophylactic antibiotics for opportunistic infections Specialty consult as appropriate	If improves to Grade \leq 1: Taper steroids over at least 1 month and resume a velumab therapy following steroids taper.
Recurrence of same Grade 3 irAEs	Permanently discontinue a velumab therapy 1.0 to 2.0 mg/kg/day prednisone or equivalent Add prophylactic antibiotics for opportunistic infections Specialty consult as appropriate	If improves to Grade \leq 1: Taper steroids over at least 1 month.
Grade 4	Permanently discontinue a velumab therapy 1.0 to 2.0 mg/kg/day prednisone or equivalent and/or other immunosuppressant as needed Add prophylactic antibiotics for opportunistic infections Specialty consult.	If improves to Grade \leq 1: Taper steroids over at least 1 month
Requirement for 10 mg per day or greater prednisone or equivalent for more than 12 weeks for reasons other than hormonal replacement for adrenal insufficiency Persistent Grade 2 or 3 irAE lasting 12 weeks or longer	Permanently discontinue a velumab therapy Specialty consult	

15.4 APPENDIX D: PERIPHERAL BLOOD AND URINE COLLECTION AND STORAGE

Blood Processing Core [name] Lab

Refer to Sections 3.7 (Study Calendar) and 5.1 for research blood and urine collection time points.

Contact: For questions, please contact [name] Pharmacology Program (CPP) at [contact]; additionally, for pre-notification of planned samples (at least 24 hours in advance, the Friday before is preferred) email [contact]. After sample collection, please page [name] for immediate pick-up. For any questions regarding sample processing, you may contact [contact] or at [contact].

Venipuncture

- Approximately 40 ml of peripheral blood will be collected into EDTA (lavender) and Streck (brown/black) tubes. The amount of blood collected will be dictated by the number of experiments to be performed. Although, above tubes are ideal for the collection, they may be substituted at the discretion of the investigator.
- cfDNA
 1. Collect blood in two 10 ml Streck Tubes
 2. Keep at room temperature until processing (Samples are stable for up to five days at room temperature and can be batched with other samples drawn on different days)
 3. All steps for plasma separation should be done in a clean space, preferably in a separate room dedicated for this procedure, but minimally without the presence of molecular biology reagents such as PCR products, plasmids or any other low complexity DNA, which will contaminate the plasma. The centrifuge used for this should not be used if the centrifuge is also used for bacteria, plasmid purification etc. Use of a 1% bleach solution to wipe down areas before and after processing (inside and outside the workspace) can greatly cut down on contamination issues. (Clorox Healthcare Bleach Germicidal Wipes - Wipe - 6" Width x 5" Length - 150 / Canister - 1 Each – White Item # 129202)
 4. In hood: transfer blood to 15 mL conical tube
 5. Centrifuge 15 mL conical tubes for 10 minutes at $1500 \pm 150 \times g$ (=1500RCF)
 6. Transfer supernatant to a fresh 15 ml tube without disturbing the leukocyte layer
 7. Centrifuge plasma a second time for 10 min at $3000 \pm 150 \times g$ (=3000 RCF)
 8. Transfer supernatant to a fresh 15 ml centrifuge tube without disturbing the cellular layer. Leave a residual volume of about 0.3 ml (~7 mm) on the bottom of the 15 ml tube to avoid cellular contamination.
 9. After transferring the plasma to a new 15 ml centrifuge tube as described, gently mix plasma and record total plasma volume (typically ~ 4 ml plasma per 10 ml blood).
 10. Make 1 mL aliquots into standard cryovials
 11. Barcode as plasma
 12. Enter sample note: cfDNA
 13. Store plasma at -80°C freezer, ship without thawing
- gDNA
 1. Collect blood in one 10 ml Lavender EDTA tube

2. Keep at room temperature until processing
 3. Follow standard procedures for DNA isolation per [name] Lab
 4. Store at -80°C freezer
- PBMC
 1. Collect blood in one 10 ml Lavender EDTA tube
 2. Keep at room temperature until processing
 3. Follow standard procedures for PBMC pellet preparation per [name] Lab
 4. Store at -80°C freezer

Urine (spot) Sample Collection

- Approximately 45 mL of urine will be collected into a standard urine collection cup for further analysis. The amount of urine collected will be dictated by the number of experiments to be performed.
- Transfer to two 50 ml screw-cap conical tubes
- Freeze immediately at -20°C or lower
- Maintain in -80°C freezer for storage until shipment

Labeling of Samples

All specimens are to be labeled per the local site's standard procedures. The following information, if not provided on the specimen label, must be linked to the specimen label and provided on the inventory sheet:

- Patient study ID #
- Sample type
- Date/time of draw (DD/MMM/YY 24:00)
- Time point (ex. C1D1 pre, C1D1 24hr post)
- Any collection issues (short draw, delayed processing, etc.)
- Protocol title/number
- Institute name
- Contact information
- Do not include the patient name, medical record number, or initials.

7. Discard supernatant of the 50 ml tube. Resuspend the pellet in 0.5 ml "MACS + BSA" buffer. Transfer all to the top of LS column until no elution out, repeat to use 0.5 ml "MACS + BSA" buffer to wash the 50 ml tube and transfer on the top of first column for three times, i.e. in total 2 ml.
8. Until no elution out of column, put the "-" 15 ml tube under second LS column. Pull out first LS column and insert it into the new "+1" 15 ml tube. Add 1 ml "MACS + BSA" buffer on top of the column. Insert syringe and quickly plunge it down. Transfer all the elution from "+1" tube on the top of second LS column. Until no elution out, repeat to use 0.5 ml "MACS + BSA" buffer to wash the "+1" tube and transfer on the top of second column for three times, i.e. in total 2 ml.
9. Until no elution out of column, pull out first LS column and insert it into the new "+2" 15 ml tube. Add 1 ml "MACS + BSA" buffer on top of the column. Insert syringe and quickly plunge it down. Use 20 ul resuspension from "+2" tube to count CD138+ cell number and 20 ul resuspension from "-" tube to count CD138- cell number.
10. Spin both "-" and "+2" tubes at 1250 rpm for 10 min. Resuspend in 0.5 ml "MACS + BSA" buffer and transfer to new 1.5 ml Eppendorf tubes as CD138- and CD138+ cells respectively.
11. Spin at 5000 rmp for 5 min. Aspirate supernatant and store it in -20°C freezer. Label on 1.5 ml Eppendorf tube with patient ID number on the first row, "CD138-" or "CD138+" as second row, cell number as third row, and date as fourth row.

15.6 APPENDIX F: IMWG RESPONSE CRITERIA

NOTE: The following are taken from the International Myeloma Working Group (IMWG) response criteria, 2016 (adapted).[\[1\]](#)

IMWG MRD criteria (requires a complete response as defined below)	
Sustained MRD-negative (Sustained MRDnegCR)	MRD negativity in the marrow (NGF or NGS, or both) and by imaging as defined below, confirmed minimum of 1 year apart. Subsequent evaluations can be used to further specify the duration of negativity (e.g., MRD-negative at 5 years)
Flow MRD-negative (Flow MRDnegCR)	Flow MRD-negative Absence of phenotypically aberrant clonal plasma cells by NGF on bone marrow aspirates using the EuroFlow standard operation procedure for MRD detection in multiple myeloma (or validated equivalent method) with a minimum sensitivity of 1 in 10 ⁵ nucleated cells or higher
Sequencing MRD-negative (Seq MRDnegCR)	Absence of clonal plasma cells by NGS on bone marrow aspirate in which presence of a clone is defined as less than two identical sequencing reads obtained after DNA sequencing of bone marrow aspirates using the LymphoSIGHT platform (or validated equivalent method) with a minimum sensitivity of 1 in 10 ⁵ nucleated cells or higher
Imaging plus MRD-negative (Img MRDnegCR)	MRD negativity as defined by NGF or NGS plus disappearance of every area of increased tracer uptake found at baseline or a preceding PET/CT or decrease to less mediastinal blood pool SUV or decrease to less than that of surrounding normal tissue

Standard IMWG response criteria	
Stringent complete response (sCR)	Complete response as defined below plus normal FLC ratio and absence of clonal cells in bone marrow biopsy by immune-histochemistry (κ/λ ratio $\leq 4:1$ or $\geq 1:2$ for κ and λ patients, respectively, after counting ≥ 100 plasma cells)
Complete response (CR)	Negative immunofixation on the serum and urine and disappearance of any soft tissue plasmacytomas and $<5\%$ plasma cells in bone marrow aspirates
Very good partial response (VGPR)	Serum and urine M-protein detectable by immunofixation but not on electrophoresis or $\geq 90\%$ reduction in serum M-protein plus urine M-protein level <100 mg per 24 h
Partial response (PR)	$\geq 50\%$ reduction of serum M-protein plus reduction in 24 h urinary M-protein by $\geq 90\%$ or to <200 mg per 24 h; If the serum and urine M-protein are unmeasurable, a $\geq 50\%$ decrease in the difference between involved and uninvolved FLC levels is required in place of the M-protein criteria; If serum and urine M-protein are unmeasurable, and serum-free light assay is also unmeasurable, $\geq 50\%$ reduction in plasma cells is required in place of M-protein, provided baseline bone marrow plasma-cell percentage was $\geq 30\%$. In addition to these criteria, if present at baseline, a $\geq 50\%$ reduction in the size (SPD)§§ of soft tissue plasmacytomas is also required

Standard IMWG response criteria	
Minimal response (MR)	≥25% but ≤49% reduction of serum M-protein and reduction in 24-h urine M-protein by 50–89%. In addition to the above listed criteria, if present at baseline, a ≥50% reduction in the size (SPD) of soft tissue plasmacytomas is also required
Stable disease (SD)	Not recommended for use as an indicator of response; stability of disease is best described by providing the time-to-progression estimates. Not meeting criteria for complete response, very good partial response, partial response, minimal response, or progressive disease
Progressive disease (PD)	Any one or more of the following criteria: Increase of 25% from lowest confirmed response value in one or more of the following criteria: Serum M-protein (absolute increase must be ≥0.5 g/dL); Serum M-protein increase ≥1 g/dL, if the lowest M component was ≥5 g/dL; Urine M-protein (absolute increase must be ≥200 mg/24 h); In patients without measurable serum and urine M-protein levels, the difference between involved and uninvolved FLC levels (absolute increase must be >10 mg/dL); In patients without measurable serum and urine M-protein levels and without measurable involved FLC levels, bone marrow plasma-cell percentage irrespective of baseline status (absolute increase must be ≥10%); Appearance of a new lesion(s), ≥50% increase from nadir in SPD of >1 lesion, or ≥50% increase in the longest diameter of a previous lesion >1 cm in short axis; ≥50% increase in circulating plasma cells (minimum of 200 cells per μL) if this is the only measure of disease

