2 ELIGIBILITY ASSESSMENT AND ENROLLMENT

2.1 ELIGIBILITY CRITERIA

2.1.1 Inclusion Criteria

2.1.1.1 Patients must have a documented diagnosis of multiple myeloma defined by the International Myeloma Working Group Criteria (IMWG)[\[3\]](#). Patients at initial diagnosis must have had a serum M-protein ≥ 3 g/dL and/or bone marrow plasma cells $\geq 10\%$, and at least one of the following:

- Anemia: Hemoglobin ≤ 10 g/dL, or
- Renal failure: serum creatinine ≥ 2.0 mg/dL, or
- Hypercalcemia: Ca ≥ 10.5 mg/dL, or
- Lytic bone lesions on X-ray, CT, or PET/CT, or
- ≥ 2 focal lesions on spinal MRI, or
- $\geq 60\%$ bone marrow plasma cells, or
- Involved/un-involved serum free light chain ratio ≥ 100

2.1.1.2 Have at least one extramedullary plasmacytoma or lytic lesion which at the discretion of the investigators is amenable to and clinically indicated for localized radiation therapy

2.1.1.3 Must have *Relapsed* or *Relapsed and Refractory* Multiple Myeloma. Patients must have documented evidence of progressive disease (PD) as defined by the IMWG criteria on or after their last regimen and must have achieved a minimal response (MR) or better to at least one prior regimen. Definitions by the IMWG:[\[93\]](#)

- Relapsed and refractory: disease that is nonresponsive while on salvage therapy or progresses within 60 days of last therapy in patients who have achieved minor response (MR) or better
- Relapsed: disease that progresses and requires the initiation of salvage therapy but does not meet criteria for either *primary refractory* or *relapsed and refractory* MM categories

2.1.1.4 Patients must have been previously treated for MM and be refractory to, not a candidate for (ineligible), or intolerant of available therapeutic regimens known to provide clinical benefit including immunomodulatory (IMiD), proteasome inhibitor, and anti-CD38 monoclonal antibody-based treatments.

2.1.1.5 Documented measurable disease within the 4 weeks prior to registration defined by any one of the following:

- Monoclonal Bone marrow plasma cells $\geq 5\%$
- Serum monoclonal protein ≥ 0.2 g/dl
- Urine monoclonal protein > 200 mg/24 hour
- Serum immunoglobulin free light chain > 10 mg/dL AND abnormal kappa/lambda ratio
- A measurable lesion on PET/CT or MRI

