10.4.2 Analysis of the Primary Endpoints

The fraction of patients who experience a PR, VGPR, CR, or sCR using the study treatment will be determined by dividing the number of responders by the total evaluable patients. The fraction will be reported along with 90% and 95% two-sided confidence intervals

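### The first limb of the VGPR row in Appendix F can be met by an unchanged baseline state, so as printed it can add non-responders to the primary ORR; how often is not known from the documents

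*Combined protocol and SAP*

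**What the plan says.** **Response table (Appendix F).** The VGPR row offers two alternatives. The first is "Serum and urine M-protein detectable by immunofixation but not on electrophoresis". Only the second, a fall of at least 90% in serum M-protein with a low urine level, describes a change. The PR row provides for patients whose serum and urine M-protein cannot be measured: a 50% or greater "decrease in the difference between involved and uninvolved FLC levels is required in place of the M-protein criteria". If FLC is unmeasurable too, it requires a 50% fall in marrow plasma cells, provided the baseline percentage was at least 30%. The VGPR row has no such provision. Stable disease is the residual category: "Not meeting criteria for complete response, very good partial response, partial response, minimal response, or progressive disease".

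**Entry (2.1.1.5).** The criterion is "Documented measurable disease within the 4 weeks prior to registration defined by any one of the following". Three of the five routes need no M-protein on electrophoresis: marrow plasma cells of 5% or more, "Serum immunoglobulin free light chain > 10 mg/dL AND abnormal kappa/lambda ratio", and "A measurable lesion on PET/CT or MRI".

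**Analysis.** Section 10.3.2 makes any patient with measurable disease at baseline and one dose evaluable for response. Section 6.3.1 takes the best response recorded from the start of treatment. Section 10.4.2 defines the primary result as "The fraction of patients who experience a PR, VGPR, CR, or sCR using the study treatment", over all evaluable patients. Section 10.2 stops the trial at 0 of 13 responses and calls the regimen interesting at 4 or more of 27.

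**The concern.** A response category should record something that happened after treatment began. The first VGPR limb does not require that. A patient enrolled on FLC, marrow or a lesion, with no M-protein on electrophoresis but a positive immunofixation, can satisfy it before the first dose and again at the first on-treatment test.

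The table is then out of order for this patient: PR demands a 50% fall in the FLC difference or in marrow plasma cells, while the deeper category demands no fall. The residual definition of stable disease gives no protection, because a patient who meets VGPR cannot be stable.

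The thresholds are low, at one response to open stage 2 and four to succeed, so a few such patients could matter. The post-cycle-1 ORR in 10.4.3 is calculated in the same way and has the same weakness.

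**Working it through.** **1. Does anything in the plan close the gap?** Following one unchanged patient through the documents:
- 2.1.1.5: eligible on FLC, marrow or a lesion.
- 10.3.2: evaluable after one dose.
- Appendix F: immunofixation positive and electrophoresis negative, so VGPR by the first limb.
- 6.3.1: recorded as best response; no exclusion for a category present at baseline.
- 10.4.2: counted in the numerator.

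No section says that VGPR presupposes PR. The plan does foresee patients without measurable M-protein: 2.2.4 asks for a 24-hour urine when serum M-protein is 0.2 g/dL or less, 2.2.6 allows a screening marrow when disease is not otherwise measurable, and the PR and PD rows have rules for such patients.

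**2. The plan's own design figures.** Inputs from 10.2: 13 patients in stage 1, stop at 0; 27 in total, success at 4 or more; null rate 5%, target rate 20%.
- Early termination at 5%: 0.95^13 = 0.5133 (the plan states 51.3%).
- Success probability = sum over x = 1 to 13 of P(X1 = x) × P(X2 ≥ 4 − x), with X1 ~ Bin(13, p) and X2 ~ Bin(14, p). This gives 0.0416 at p = 0.05 and 0.8011 at p = 0.20.

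The stated design is reproduced.

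**3. A fixed number k of baseline-VGPR patients among the 27 places.** Assumptions: each is scored VGPR, all others respond at 5%, and the k places fall at random across the two stages.

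| k | At least one in stage 1 | All in stage 2 | Chance that all are in stage 2 | Overall success probability |
|---|---|---|---|---|
| 0 | – | – | – | 0.042 |
| 1 | ≥3 of the other 26: 0.1386 | 0.1261 | 14/27 = 0.5185 | 0.132 |
| 2 | ≥2 of the other 25: 0.3576 | 0.2969 | (14×13)/(27×26) = 0.2593 | 0.342 |
| 3 | ≥1 of the other 24: 1 − 0.95^24 = 0.708 | 1 − 0.5133 = 0.4867 | (14×13×12)/(27×26×25) = 0.1244 | 0.680 |

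For example, k = 2: 0.7407 × 0.3576 + 0.2593 × 0.2969 = 0.342. With one such patient among the first 13, the count cannot be 0, so the probability of early termination falls from 0.513 to 0.

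**4. The same by share.** Let f be the probability that an evaluable patient is in this state at entry and is scored as printed. The documents do not give f, so it is an assumption. The apparent null rate is f + (1 − f) × 0.05.

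| f | Apparent null rate | Success probability |
|---|---|---|
| 0 | 0.050 | 0.042 |
| 2% | 0.069 | 0.107 |
| 5% | 0.0975 | 0.256 |
| 10% | 0.145 | 0.547 |

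**The case against.** Four points can be made for the plan.

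- **The group is narrow.** The limb names serum and urine together. Read literally, a patient must be immunofixation positive and electrophoresis negative in both fluids. A patient positive in only one, or negative on immunofixation, does not meet it. The serum M-protein entry threshold is only 0.2 g/dL, so many patients will have a visible band. This stands, and it limits how often the problem can arise.
- **The wording elsewhere implies change.** Section 10.4.2 speaks of patients who experience a response using the study treatment, 6.3.2 ranks responses as PR or better, and 2.1.1.3 requires documented progression at entry. An assessor who treats the categories as ordered would not score an unchanged patient as VGPR. This is a sensible reading, but it is an inference that no section states, and the residual definition of stable disease points the other way.
- **The cited criteria may contain more.** Section 6.3 names the 2016 IMWG criteria, and Appendix F is marked as adapted. Whether the source restricts this limb cannot be checked here; the plan sends its reader to the appendix.
- **The size is assumed.** This stands. The 5% and 10% shares have no anchor in the documents, and every figure supposes that assessors score the unchanged patient as VGPR.

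A reader might infer from the table that the 5% error rate is already lost, or that patients measured by FLC, marrow or lesion count as responders in general. The documents support neither. The first needs a frequency and a scoring practice that they do not give; the second ignores the immunofixation and two-fluid conditions.

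**Conclusion.** The VGPR row is wrong as written. Its first limb needs no change from baseline, it lacks the PR row's substitution, and no other section stops the resulting category from entering the primary ORR and both decision rules.

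The consequence is conditional. It requires that patients already in this state, literally in both fluids, enrol, and that they are scored as the table reads. Under those two conditions and a true 5% rate in all other patients, one, two or three among 27 give a false-positive probability of about 13%, 34% or 68%, against 4.2% as designed. If none enrol, or if assessors already require a change, the design keeps its stated properties: type I error 0.042, power 0.80, early termination 51.3%. Because a single patient can triple the error rate and cancel the futility stop, the wording should be settled before response is assessed.

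**What to change.** - In Appendix F, state that the immunofixation-only limb of VGPR applies only if M-protein was measurable on electrophoresis at baseline. Patients with unmeasurable M-protein are then assessed under the PR row's printed substitution.
- In 10.4.2, state that a category already met at baseline is not a response. The post-cycle-1 ORR in 10.4.3 follows the same rule.

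No FLC threshold for VGPR is proposed. Carrying the row's 90% figure over to FLC may look natural, but the documents contain no such rule.

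**Cost.** This is wording only. The myeloma tests are already in the Study Calendar (3.7), and the sample size need not change. The ORR may be lower. There is also a gap to resolve: the marrow substitution in the PR row needs at least 30% plasma cells at baseline, while 2.1.1.5 admits patients at 5% or on a lesion alone. Those whose M-protein and FLC are unmeasurable and whose marrow is below 30% have no printed PR route, yet stay in the denominator under 10.3.2. The documents do not give their share, so the effect on power cannot be stated. The sponsor should reconcile Appendix F with 2.1.1.5 and 10.3.2 in the same amendment.
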